## **4. Treatment retention time**

If a subject’s reason for withdrawal from Post-1-Year Open-Label Period included: withdrawal of consent, lost to follow-up, physician decision or other, then it will be assumed the subject terminated due to lack of efficacy. For subjects that discontinue due to adverse event or lack of efficacy, the treatment retention time during Post-1-Year Open-Label Period will be calculated as the date of last known dose during Post-1-Year Open-Label Period minus the date of the first dose of eslicarbazepine acetate monotherapy in protocol 093-045 or 093-046 (Visit 6/Week 8), plus 1. The time may include taking eslicarbazepine acetate concomitantly with other AEDs.

**5.2.4. Entire Open-Label Period Endpoints**

**1. Change in Quality of Life in Epilepsy**

The QOLIE-31 contains seven multi-item scales that assess the following health concepts: emotional well-being, social functioning, energy/fatigue, cognitive functioning, seizure worry, medication effects, and overall quality of life. The QOLIE-31 overall score is obtained by using a weighted average of the multi-item scale scores. The QOLIE-31 also includes a single item that assesses overall health on a visual analogue scale. The recorded responses will be converted to 0-100 point scales as described in Table 1. The mean of the individual item scores in each subgroup are then calculated, with higher converted scores reflecting better quality of life. If one item within a scale score is missing, it will be replaced by the mean value of the other items. If more than one item is missing, the scale score will not be calculated.

The QOLIE-31 overall score is obtained by using a weighted average of the 7 scale scores according to the following formula:

$$\begin{aligned} \text{Overall score} &= \text{Seizure worry} * 0.08 \\ &+ \text{Overall quality of life} * 0.14 \\ &+ \text{Emotional well-being} * 0.15 \\ &+ \text{Energy/fatigue} * 0.12 \\ &+ \text{Cognitive functioning} * 0.27 \\ &+ \text{Medication effects} * 0.03 \\ &+ \text{Social functioning} * 0.21 \end{aligned}$$

If no score has been calculated for at least one of the 7 scales, the overall QOLIE-31 score will not be calculated. The change from baseline to each post-treatment assessment in QOLIE-31 overall score will also be calculated.

**Table 1: QOLIE-31 Response Conversions**

Scale	Response						Formula	
	Item Numbers	1	2	3	4	5		6
Seizure Worry								
11.		0	20	40	60	80	100	$((\text{Resp}-1)/(\text{Max}-1))*100$
21.		0	33.3	66.7	100	-	-	$((\text{Resp}-1)/(\text{Max}-1))*100$
22.		0	50	100	-	-	-	$((\text{Resp}-1)/(\text{Max}-1))*100$
23.		0	33.3	66.7	100	-	-	$((\text{Resp}-1)/(\text{Max}-1))*100$

25. 100 75 50 25 0 -  $100 - ((\text{Resp}-1)/(\text{Max}-1)) * 100$

**Overall Quality of Life**

1. Multiply response by 10

14. 100 75 50 25 0 -  $100 - ((\text{Resp}-1)/(\text{Max}-1)) * 100$

**Emotional Well-being**

3. 0 20 40 60 80 100  $((\text{Resp}-1)/(\text{Max}-1)) * 100$

4. 0 20 40 60 80 100  $((\text{Resp}-1)/(\text{Max}-1)) * 100$

5. 100 80 60 40 20 0  $100 - ((\text{Resp}-1)/(\text{Max}-1)) * 100$

7. 0 20 40 60 80 100  $((\text{Resp}-1)/(\text{Max}-1)) * 100$

9. 100 80 60 40 20 0  $100 - ((\text{Resp}-1)/(\text{Max}-1)) * 100$

**Energy/Fatigue**

2. 100 80 60 40 20 0  $100 - ((\text{Resp}-1)/(\text{Max}-1)) * 100$

6. 100 80 60 40 20 0  $100 - ((\text{Resp}-1)/(\text{Max}-1)) * 100$

8. 0 20 40 60 80 100  $((\text{Resp}-1)/(\text{Max}-1)) * 100$

10. 0 20 40 60 80 100  $((\text{Resp}-1)/(\text{Max}-1)) * 100$

**Cognitive Functioning**

12. 0 20 40 60 80 100  $((\text{Resp}-1)/(\text{Max}-1)) * 100$

15. 0 33.3 66.7 100 - -  $((\text{Resp}-1)/(\text{Max}-1)) * 100$

16. 0 20 40 60 80 100  $((\text{Resp}-1)/(\text{Max}-1)) * 100$

17.	0	20	40	60	80	100	$((\text{Resp}-1)/(\text{Max}-1))*100$
18.	0	20	40	60	80	100	$((\text{Resp}-1)/(\text{Max}-1))*100$
26.	100	75	50	25	0	-	$100-((\text{Resp}-1)/(\text{Max}-1))*100$

**Medication Effects**

24.	0	33.3	66.7	100	-	-	$((\text{Resp}-1)/(\text{Max}-1))*100$
29.	100	75	50	25	0	-	$100-((\text{Resp}-1)/(\text{Max}-1))*100$
30.	100	75	50	25	0	-	$100-((\text{Resp}-1)/(\text{Max}-1))*100$

**Social Functioning**

13.	0	20	40	60	80	100	$((\text{Resp}-1)/(\text{Max}-1))*100$
19.	0	25	50	75	100	-	$((\text{Resp}-1)/(\text{Max}-1))*100$
20.	0	25	50	75	100	-	$((\text{Resp}-1)/(\text{Max}-1))*100$
27.	100	75	50	25	0	-	$100-((\text{Resp}-1)/(\text{Max}-1))*100$
28.	100	75	50	25	0	-	$100-((\text{Resp}-1)/(\text{Max}-1))*100$

Resp=Response, Max=Maximum possible response for the respective item.

Change in Quality of Life is defined as the change in QOLIE-31 total score from Visit 2 (Day 0) of Protocols 093-045 or 093-046 to end of study treatment (ET/EOS).

**2. Change in Montgomery-Asberg Depression Rating Scale**

The MADRS measures the effect of study drug on depression severity by assessing the severity of 10 symptoms on a scale from 0 (best score) to 6 (worst score), including:

- Apparent sadness
- Reported sadness
- Inner tension
- Reduced sleep
- Reduced appetite
- Lassitude
- Concentration difficulties
- Suicidal thoughts
- Inability to feel
- Pessimistic thoughts

The total score is defined as the sum of all individual item scores. If one item is missing at a given visit, it will be replaced with the mean of the answers that are present. If more than one item is missing at a given visit, no total score will be calculated.

Change in MADRS total score will be summarized from Visit 2 (Day 0) of Protocols 093-045 or 093-046 (baseline) to end of study treatment (ET/EOS). This analysis will be repeated for subjects with a MADRS score of  $\geq 14$  at screening visit (Visit 1) of the present study.

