### 2.2. Secondary objectives

- To evaluate the maintenance of the therapeutic effects of eslicarbazepine acetate over a 1-Year Open-Label Period and Post-1-Year Open-Label Period.
- To evaluate the health-related quality-of-life, suicidality, and depressive symptoms over a 1-Year Open-Label Period and Post-1-Year Open-Label Period.

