Abbreviations: A=Electronic Data Capture (Inform); B=Laboratory Information Management System (LIMS); C=Core Lab Over-Read; C-SSRS=Columbia Suicidality Severity Rating Scale; EOS=End of Study; ET=Early Termination; MADRS=Montgomery-Asberg Depression Rating Scale; NTx=N-telopeptides of type I collagen cross-links; SCN=Screening; 25-OHD=25-hydroxyvitamin D; TSH=thyroid stimulating hormone; PGI=Patient Global Impression; PTH=parathyroid hormone; QOLIE-31=31-Item Quality of Life in Epilepsy.

- a. Demographic information, medical history, psychiatric history, medication history, magnetic resonance imaging/computerized tomography scans, electroencephalogram data, HLA-B\*1502 genotyping, and Hepatitis B/C screen results collected during the screening visit of Protocols 093-045 or 093-046 will apply for this study as well.
- b. Clinic visits to occur at intervals of 3 months during the post-1-year part.
- c. Letters in this column identify the computerized systems that will be used in this protocol (Appendix IX in protocol).
- d. The symbol “•” represents procedures performed at Visit 9 of Protocols 093-045 or 093-046, the results of which will apply to Visit 1 of the present study as well. These procedures do not have to be repeated.
- e. In street clothes without shoes and jacket/coat.
- f. Fasting labs.
- g. These assessments are not required to be performed if this visit falls in the post-1-year part of the study.
- h. If this visit falls in the post-1-year part of the study, this assessment may be performed only if clinically indicated (per Investigator judgement on a previously noted abnormality).
- i. Includes serum 25-OHD, PTH, osteocalcin, bone-specific alkaline phosphatase, and urinary NTx.
- j. At Visit 5 only.
- k. Every 6 months (i.e. Visits 7, 9, 11, 13, etc.).
- l. Only in subjects ≥18 years at time of signing informed consent in Protocols 093-045 or 093-046.
- m. Only for subjects who discontinue study during the post-1-year part of study.
- n. Fill out “since last visit” scale (Appendix VII in protocol).
- o. Only for subjects who discontinue study during the 1-year part of study.
- p. Only for subjects who continue into the post-1-year part of the study.

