### **Baseline**

Change in seizure related efficacy parameters will be calculated with reference to the baseline period defined as the baseline period (From Visit 1 to Visit 2) from protocol 093-045 and 093-046. The change in QOLIE, MADRS and safety parameters will be calculated with reference to the baseline as Day 0 (Visit 2) for protocol 093-045 and 093-046.

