### **Change in Montgomery-Asberg Depression Rating Scale (MADRS)**

The total MADRS score and the 10 individual items will be summarized descriptively for each evaluation visit, along with the change from baseline (Visit 2, Day 0 from protocol 093-045 or 093-046).

In addition, this analysis will be repeated for those subjects with a MADRS score of  $\geq 14$  at screening (Visit 1) of this study. A listing of subjects with MADRS assessments will be provided.

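### The MADRS subgroup is selected at extension Visit 1 but its change is measured from parent-study Day 0, so the summary describes neither baseline-depressed subjects nor the open-label course

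*SAP*

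**What the plan says.** Selection: SAP 5.2.4 (item 2) repeats the MADRS change analysis in subjects with a score of at least 14 "at screening visit (Visit 1) of the present study". The MADRS paragraph of SAP 7.6 gives the same rule, "at screening (Visit 1) of this study".

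Reference: both places take change from parent Visit 2 (Day 0), and the Baseline paragraph of SAP 6.1 makes this general: "The change in QOLIE, MADRS and safety parameters will be calculated with reference to the baseline as Day 0 (Visit 2").

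Source of the Visit 1 score: the schedule in SAP 5.1 marks MADRS at Visit 1 with a bullet. Footnote d says that the bullet "represents procedures performed at Visit 9 of Protocols 093-045 or 093-046, the results of which will apply to Visit 1 of the present study". The note to the study schematic (SAP 3.2) also equates the two visits.

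Objective: SAP 2.2 includes "To evaluate the health-related quality-of-life, suicidality, and depressive symptoms over a 1-Year Open-Label Period and Post-1-Year Open-Label Period".

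The SAP gives no reason for using different visits. It plans neither a Day 0-selected version nor a change from Visit 1. The subgroup lists in SAP 6.5 do not cover MADRS, so this is the only MADRS subgroup summary.

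**The concern.** The selecting score is itself a post-baseline measurement of the variable being summarised. Two problems follow.

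- **Membership depends on the change.** A subject with 24 at Day 0 and 10 at Visit 1 is excluded; one with 6 and then 18 is included. The group is therefore not the set of subjects who had high scores before parent-study treatment.
- **The period is mixed.** The change adds the Day 0 to Visit 1 segment, which precedes this study, to the open-label segment that the objective names.

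At stake is how a secondary-objective table is read. A reader would probably take it as the course of depressive symptoms in subjects who were depressed at the outset, or as what open-label treatment did for those depressed at entry. It is neither.

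**Working it through.** **Inputs from the documents.** Cut-off 14; selection at Visit 1, which is parent Visit 9; reference at parent Day 0. The gap is up to 18 weeks (SAP 3.1), consistent with monotherapy starting at Week 8 (SAP 5.2.2) plus 10 weeks of double-blind monotherapy (SAP 6.5). The documents give no MADRS mean, SD, correlation or subgroup size, so there is no planned figure to reproduce.

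**Step 1: individual scores, no assumptions needed.** Both subjects below score at least 14 at Visit 1 and so are in the subgroup.

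| Day 0 | Visit 1 | End | Reported (End - Day 0) | Open-label (End - Visit 1) |
|---|---|---|---|---|
| 8 | 20 | 12 | 12 - 8 = +4 | 12 - 20 = -8 |
| 24 | 15 | 22 | 22 - 24 = -2 | 22 - 15 = +7 |

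In each case the reported sign is opposite to the open-label change.

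**Step 2: direction of the group mean.** Write B, S and E for the scores at Day 0, Visit 1 and end of study, and r for their correlations. Assume normal scores with equal SDs and no true mean change. Let m be the mean score of the selected group at the selecting visit, minus the population mean.

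- Planned, at end of study: (r_SE - r_BS) × m
- Planned, at Visit 1 itself: (1 - r_BS) × m
- Selected at Day 0, change from Day 0: -(1 - r_BE) × m
- Selected at Visit 1, change from Visit 1: -(1 - r_SE) × m

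For an assumed mean of 10 and SD of 7, whole-number scores put the cut at 13.5, so z = (13.5 - 10)/7 = 0.5 and m = 7 × 0.3521/0.3085 = 7.99.

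| r_BS, r_SE, r_BE | Planned, end | Planned, Visit 1 | Day 0-selected | From Visit 1 |
|---|---|---|---|---|
| 0.6, 0.6, 0.6 | 0.0 | 0.4 × 7.99 = +3.2 | -3.2 | -3.2 |
| 0.6, 0.4, 0.3 | -0.2 × 7.99 = -1.6 | +3.2 | -0.7 × 7.99 = -5.6 | -0.6 × 7.99 = -4.8 |
| 0.5, 0.7, 0.4 | +0.2 × 7.99 = +1.6 | 0.5 × 7.99 = +4.0 | -0.6 × 7.99 = -4.8 | -0.3 × 7.99 = -2.4 |

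Planned minus Day 0-selected is (1 - r_BS + r_SE - r_BE) × m. This is positive whenever Visit 1 predicts the end score at least as well as Day 0 does (r_SE ≥ r_BE), which is what time order would suggest.

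**Step 3: wider range.** Simulation of 63 assumed scenarios: mean/SD 8/7, 10/7 and 12/8; r_BS and r_SE from 0.4 to 0.7; r_BE from 0.3 to 0.7; true mean change by Visit 1 of -2, 0 or +2 and none after; scores rounded and held within 0 to 60.

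- Subjects at 14 or more on Day 0 who are left out: 19% to 72%.
- Planned subgroup members below 14 on Day 0: 24% to 64%.
- Planned minus Day 0-selected, end of study: +2.2 to +8.5 points.
- Planned change at Visit 1 itself: about +0.6 to +6.7 points.
- Planned minus all subjects, end of study: -2.5 to +1.9 points.

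**The case against.** The strongest defence is that separating the selecting visit from the reference visit protects against regression to the mean. With equal correlations and no true change, the planned end-of-study mean is about 0, while both aligned versions show a spurious improvement of about 3.2 points. This stands as a warning about the remedy. It does not rescue the plan: the cancellation depends on correlations that nobody has stated, and it repairs neither the membership nor the mixed period.

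Second, SAP 7.6 summarises scores at each evaluation visit and plans a listing. If Visit 1 is displayed as one of those visits, the subgroup's open-label course can be worked out from the observed means. This stands in part, but the planned change column would still be measured from Day 0.

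Third, parent Day 0 is the SAP-wide reference for QOLIE-31, MADRS and safety. That explains the reference visit, not the selection visit.

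Fourth, the stakes are modest, and this stands. The analysis is descriptive, with no test or sample size resting on it. The ITT MADRS summary includes everyone, and suicidality is assessed by the C-SSRS, with its own shift table.

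**Conclusion.** The mismatch is real and follows from the SAP text alone. The subgroup is selected on a post-baseline value of its outcome, and the reported change can have the opposite sign to an individual's open-label change.

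Relative to a Day 0-selected subgroup, the result is shifted towards worsening: by 2.2 to 8.5 points at end of study over the assumed scenarios. That comparator is itself pulled towards improvement by regression to the mean.

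A reader might infer that the planned result is biased towards worsening outright, or that it hides a true improvement. The documents do not support this. Relative to all subjects at end of study, the sign follows r_SE - r_BS when there is no true change. Day 0 and Visit 1 are at most 18 weeks apart, whereas for completers the end of study is a year or more after Visit 1. If correlation weakens with time, the shift is towards improvement. A model in which each subject's on-drug shift is permanent does give worsening, but only by construction: the shift is then proportional to the variance of that permanent component.

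Two further readings go too far. Visit 1 scores cannot be called on-treatment for everyone, because subjects who discontinued or exited the parent study may enter. The SAP also never labels the subgroup as subjects with depression.

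The impact is limited to one descriptive subgroup summary of a secondary objective.

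**What to change.** In SAP 5.2.4 (item 2) and the MADRS paragraph of 7.6, use the same visit for selection and reference. Either:

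1. define the subgroup as MADRS total of 14 or more at parent Visit 2 (Day 0) and keep change from Day 0; or
2. keep the Visit 1 subgroup, measure change from Visit 1 of 093-050, and label it change during open-label treatment. The change from Day 0 may stay as a secondary column.

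With either option, add an ITT shift table of below 14 versus 14 or more at parent Day 0, by the same categories at each MADRS visit and at EOS/ET. It shows resolved and new high scores together without selecting on the outcome.

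State next to the subgroup table that an aligned subgroup will show apparent improvement from regression to the mean, so its mean change should not be read as a drug effect. At mean 10 and SD 7, this is (1 - 0.7) × 7.99 = 2.4 to (1 - 0.6) × 7.99 = 3.2 points for correlations of 0.7 to 0.6 between the reference and end scores, and more if they are weaker. This is a real limitation of the remedy, which is why the shift table is needed.

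The cost is SAP wording and one or two tables from data already collected.

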### 5.3. Safety Assessments and Endpoints

#### 5.3.1. Safety Assessments

Adverse events will be monitored throughout the study, starting at Visit 1.

Clinical laboratory tests to be collected include: serum chemistry, hematology, thyroid panel (free T3, free T4, and TSH), coagulation testing (prothrombin time [PT]/international normalized ration [INR] and partial thromboplastin time [PTT]), lipid panel (total cholesterol, high-density lipoprotein [HDL]-cholesterol, low-density lipoprotein [LDL]-cholesterol, and triglycerides), bone turnover markers (serum 25-hydroxyvitamin D [25-OHD], parathyroid hormone [PTH], osteocalcin, bone-specific alkaline phosphatase, and urinary N-telopeptides of type I collagen cross-links [NTx]), and urinalysis.

A 12-lead ECG collect ventricular heart rate, QT interval, P-R interval, QRS durations, R-R interval, and the QTc intervals corrected by Bazett (QTcB) and Fridericia (QTcF).

Vital signs include standing and supine systolic and diastolic blood pressure, standing and supine heart rate, respiration rate, weight, and body temperature.

Physical and neurological examinations will be conducted at Visit 1 and the End of Study or Early Termination Visit.

The C-SSRS is an instrument designed to systematically assess and track suicidal events (suicidal behavior and suicidal ideation) throughout the study. The C-SSRS includes the following four sections: Suicidal Ideation, Intensity of Ideation, Suicidal Behavior and Actual Suicide Attempts. The C-SSRS will be completed by the Investigator or Sub-Investigator (or qualified site personnel).

### 5.3.2. Safety Endpoints

#### Adverse Events

All AEs will be coded using Medical Dictionary for Regulatory Activities (MedDRA), Version 13.1.

Treatment-emergent adverse events (TEAEs) will be defined as:

- AEs that occurred on or after the first dose of study drug during this protocol,
- AEs with a missing start date and a stop date on or after the first dose of study drug during this protocol, or
- AEs with both a missing start and stop date.

Adverse events whose relationship is assessed as “not related” will be grouped as “unrelated.” Otherwise, adverse events assessed as “unlikely,” “possible,” “probable,” or “definite,” unknown or missing will be grouped as “potentially related.” Further, if a subject reports more than one AE within the same treatment regimen, system organ class (SOC) and preferred term (PT), and any are related, it will be summarized as related.

If a subject has more than one occurrence of an event within a SOC and/or PT, the subject incidence summaries will count each subject only once within that SOC and/or PT. In the case of more than one event within a SOC and/or PT, the event with the highest severity will be summarized in the by-severity summaries and the one with the strongest relationship will be summarized in the by-relationship summaries.

TEAEs will be sorted by SOC in alphabetical order and then by PT sorted by decreasing frequency, with preferred terms with the same frequency sorted in alphabetical order.

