### 2.1. Primary objective

To evaluate the 1-Year Open-Label Period and Post-1-Year Open-Label Period safety and tolerability of eslicarbazepine acetate flexible dosing within the range of 800 mg to 2400 mg in subjects with partial epilepsy who have participated in an 18-week double-blind eslicarbazepine acetate monotherapy study (Protocols 093-045 or 093-046).

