## 3. Study design

### 3.1. General Description

This study is a long-term, multicenter, open-label, safety extension study in male and female subjects (aged 16 to 70 years, inclusive) with partial onset seizures who have just completed, discontinued, or exited the 18-week treatment phase of Protocols 093-045 or 093-046. The initial study duration is 1-Year Open-Label Period with the option of continuing study drug treatment Post-1-Year Open-Label Period until a subject discontinues study, the study drug becomes clinically available in the subject's locale, or the sponsor terminates the study drug clinical development program.

This study will evaluate the safety and maintenance of effect of long-term eslicarbazepine acetate treatment at flexible doses in the range of 800 mg to 2400 mg once-a-day (QD) over a 1-Year Open-Label Period and a Post-1-Year Open-Label Period.

[figure not shown]

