### **7.7.1 Adverse Events**

The following TEAEs will be summarized by MedDRA SOC and PT:

- All AEs (including number of events and subject incidence)
- AEs by severity (mild, moderate, severe)
- All serious adverse events (SAE)
- All AEs by relationship to treatment (unrelated, or potentially related)
- AEs leading to death
- AEs leading to discontinuation

All above AEs and the AE subgroup analyses in Section 6.5 will be summarized for the three periods as below.

- Year Open-Label Period
- Post-1-Year Open-Label Period
- Combined 1-Year Open-Label Period and Post-1-Year Open-Label Period

A listing of AEs, serious AEs, and AEs leading to discontinuation or death will be presented as appropriate.

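### The TEAE definition has no limb for parent-study adverse events that worsen on open-label drug, so such events may be missing from the primary safety tables

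*SAP*

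**What the plan says.** SAP 5.3.2 (Adverse Events) gives three alternative routes to TEAE status:

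1. "AEs that occurred on or after the first dose of study drug during this protocol";
2. "AEs with a missing start date and a stop date on or after the first dose of study drug during this protocol";
3. "AEs with both a missing start and stop date".

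SAP 7.7.1 opens its list of tables with "The following TEAEs will be summarized by MedDRA SOC and PT". The list covers all events, severity, serious events, relationship, death and discontinuation, each for the 1-year period, the post-1-year period and the two combined. The listings are worded more widely: "A listing of AEs, serious AEs, and AEs leading to discontinuation or death will be presented as appropriate".

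SAP 2.1 makes the primary objective the "safety and tolerability of eslicarbazepine acetate flexible dosing within the range of 800 mg to 2400 mg". SAP 3.1 takes in subjects "who have just completed, discontinued, or exited the 18-week treatment phase of Protocols 093-045 or 093-046".

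**The concern.** This is a rollover study, so some subjects can be expected to enter with an adverse event still running from the parent trial. In the schedule of evaluations (SAP 5.1), the Visit 1 adverse event entry carries the symbol for results taken over from Visit 9 of the parent study. After the first week the investigator may keep, raise or lower the dose (SAP 3.1). Worsening of an existing event after the first 093-050 dose is therefore a plausible form of harm.

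A TEAE definition usually has a clause for this case, and this one does not. At stake are the incidence, severity, seriousness and discontinuation tables for the primary objective. A carried-over event that turned severe or serious under open-label treatment could be absent from all of them.

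**Working it through.** No figure in the plan bears on this, so the check is to apply the three limbs to each kind of record and see where it falls.

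**What *occurred* means.** The SAP does not define it. Limb 2 makes separate provision for a missing start date, which would be unnecessary unless limb 1 were decided on start date. Onset is therefore the natural reading, but it remains an inference.

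**Classification on that reading**

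| Record | Limb met | TEAE? |
|---|---|---|
| (a) Start on or after first 093-050 dose | 1 | Yes |
| (b) Start missing, stop on or after that dose, even if it began in the parent study | 2 | Yes |
| (c) Start and stop both missing | 3 | Yes |
| (d) Known earlier start, ongoing, unchanged | none | No |
| (e) Known earlier start, worsens on open-label drug, kept as one record with its original start date | none | No |
| (f) As (e), but the worsening is entered as a new record with a new start date | 1 | Yes |

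Excluding (d) is appropriate. The gap is (e).

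**Comparing (b) with (e).** Take one parent-study event that stops after the first open-label dose. If its start date is lost, it counts as a TEAE even if nothing changed. If its start date is complete, it does not count, even if it became severe. Inclusion then depends on how complete the date is and not on what happened under treatment.

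**Whether another rule rescues (e).** SAP 5.3.2 puts the most severe event into the by-severity table when a subject has several in the same class or term. That rule chooses among events already admitted and does not bring in a record that failed all three limbs. Nothing else in the SAP addresses worsening of an ongoing adverse event.

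**Where (e) would and would not appear**

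- Absent: every summary table in SAP 7.7.1.
- Possibly present: the adverse event listings (7.7.1), which are not limited to TEAEs.
- Present if the event ends treatment: reasons for discontinuation (7.2), and treatment retention (5.2.2, 5.2.3, 7.6), which works from the withdrawal reason.

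A worsening that ends treatment could thus be counted in disposition and retention but not among TEAEs leading to discontinuation, so the outputs would not reconcile.

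**Size.** This would need the number of subjects with an event ongoing at rollover, the fraction of those that worsen, and the fraction of worsenings kept on the original record. The documents give none of these. If worsening is always entered as in (f), the last fraction is zero and nothing is lost.

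**The case against.** The strongest reply is that the answer may lie in a document not available here. Whether worsening becomes a new record is normally settled in the protocol body or the CRF instructions. The SAP is based on protocol version 6.0, but the public protocol document contains only the amendment history. Silence in the available text is weak evidence that no rule exists. This stands, and it makes the omission conditional. It does not remove the need for the SAP to state or cite the rule, because its tables depend on it.

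The second reply is that such events would not vanish from the report. Listings, disposition and retention are not filtered on TEAE status, and laboratory, ECG and vital-sign changes are measured from the parent-study baseline (SAP 6.1). This also stands, but none of these outputs gives adverse event incidence by term, severity or seriousness.

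Some stronger readings are tempting and are not supported:

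- *The rule can only undercount.* Limbs 2 and 3 admit events with missing dates, some of which may have begun in the parent study, so it can also overcount. The error runs one way only for fully dated events that worsen.
- *Every subject arrives after 18 weeks of treatment.* SAP 3.1 also admits subjects who discontinued or exited that phase.
- *Worsening is to be expected because dose goes up at entry.* SAP 3.1 allows the dose to stay, rise or fall, and the parent-study doses are not given, so a net rise in exposure cannot be shown.

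**Conclusion.** The point holds as a conditional gap. On the natural reading of *occurred*, an adverse event with a known parent-study start that worsens on open-label drug, and is kept as a single record, meets no limb of the TEAE definition and is absent from every summary table in SAP 7.7.1. A reader might infer that such events are certainly left out. The documents do not support that, because the recording rule cannot be seen.

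The number of subjects affected cannot be computed and could be zero. Any figure would rest on assumed rates of ongoing events and of worsening. The conclusion rests on two assumptions: that *occurred* means onset, and that at least some worsening stays on the original record. The gap still deserves correction, because it sits in the definition behind the primary safety tables, treats complete and incomplete dates inconsistently, and is cheap to close.

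**What to change.** In SAP 5.3.2:

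1. Define *occurred* in limb 1 by the event's start date.
2. Add a limb: adverse events that began before the first 093-050 dose and increased in severity or became serious on or after it.
3. For these events, use the worst post-dose severity in the by-severity table, and assign the event to the period (1-year or post-1-year) in which it worsened.
4. If worsening is already recorded as a new adverse event, state that instead and cite the rule.

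A carried-over event that leads to discontinuation without worsening should not be reclassified as a TEAE. Show it separately, for example in a footnote or an extra row of the discontinuation table, so that the table reconciles with disposition.

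The cost is one bullet and one derived flag. The flag needs dated changes in severity or seriousness in the adverse event record, and the available documents do not show that these are collected. TEAE counts may rise slightly. If the new limb is adopted where worsening is also re-entered, subject incidence is not inflated, since each subject counts once per class and term. SAP 7.7.1 also reports numbers of events, so one worsening should not be flagged on two records.
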